## PROTOCOL SYNOPSIS

INVESTIGATIONAL PRODUCT	Nab-Sirolimus, ABI-009, sirolimus protein-bound nanoparticles for injectable suspension (albumin bound), nab -rapamycin, nanoparticle albumin-bound rapamycin
FDA APPROVED STUDY AGENT	Pazopanib (VOTRIENT®), is a kinase inhibitor indicated for the treatment of subjects with 1) advanced renal cell carcinoma, and 2) advanced soft tissue sarcoma (STS) who have received prior chemotherapy
INDICATION	Previously treated subjects with advanced (metastatic or locally advanced) nonadipocytic STS, for which surgery is not an option
TITLE	A phase 1/2 study of nab-Sirolimus (ABI-009, nab -rapamycin) with pazopanib (VOTRIENT®) in subjects with advanced nonadipocytic soft-tissue sarcomas
PROTOCOL NUMBER	CC10015
PHASE OF DEVELOPMENT	1/2
STUDY OBJECTIVES	
Objectives in Phase 1
 
Primary
 

• To identify the recommended phase 2 dose (RP2D) of nab-Sirolimus given intravenously (IV) plus continuous daily oral pazopanib, for subjects with nonadipocytic STS

 
Secondary
 

• To evaluate the safety profile of the nab-Sirolimus plus pazopanib combination therapy in advanced nonadipocytic STS

 
Objectives in Phase 2
 
Primary
 

• To evaluate the efficacy of the combination of nab-Sirolimus and pazopanib at the RP2D

 
Secondary
 

• To evaluate the safety profile and to further evaluate the efficacy of nab-Sirolimus plus pazopanib combination therapy

	
Exploratory
 

• To study the correlation of clinical outcomes with Next Generation Sequencing and Immunohistochemical analyses of tumor biomarkers, including baseline secreted protein acidic and rich in cysteine (SPARC) expression.

• To assess baseline tumoral immune parameters, including PD-1, PD-L1, mutational burden, and infiltrating lymphocytes, in correlation with clinical outcomes.

STUDY ENDPOINTS	
Endpoints in Phase 1
 
Primary Endpoint
 

• Dose-limiting-toxicities (DLTs), used to estimate the maximum-tolerated dose (MTD) of nab-Sirolimus in combination with pazopanib, where the MTD is defined as the highest dose where <math>\leq 1</math> of 6 (or 0 of 3) subjects experience a DLT, thus a target DLT rate of roughly 17%.

 
Secondary Endpoint
 

• Adverse Events profile (based on National Cancer Institute [NCI] Common Terminology Criteria for Adverse Events [CTCAE] v5.0) of all subjects and each dose cohort

 
Endpoints in Phase 2 – data both from Phase 1 and 2
 
Primary Endpoint
 

• Progression-free survival (PFS) rate at 3 months, based on Response Evaluation Criteria in Solid Tumors (RECIST) v1.1

 
Secondary Endpoint
 

• Adverse Events profile (based on NCI CTCAE v5.0)

• Median PFS, PFS rate at 6 months, based on RECIST v1.1

• Median overall survival (OS), OS at 12 months

• Objective response rate (ORR) based on Response Evaluation Criteria in Solid Tumors (RECIST) v1.1

• Disease control rate (DCR), defined as complete response (CR) plus partial response (PR) plus stable disease (SD) <math>\geq 18</math> weeks, based on RECIST v1.1

• Duration of response

 
Exploratory endpoints

	

• Optional pre-treatment tumor tissue collection (fresh or archival) for biomarker analysis:

1. Correlation of genetic profiling and tissue biomarker analysis with clinical benefit

2. Correlation of baseline secreted protein acidic and rich in cysteine (SPARC) expression with clinical benefit

3. Correlation of baseline immune parameters with clinical benefit

STUDY DESIGN	
This is an open label, dose-finding, single-arm, prospective phase 1/2 study to identify the RP2D of nab-Sirolimus given IV on either Day 1 and Day 8 (qw2/3), or Day 1 only of a 21-day cycle (qw1/3), plus daily oral pazopanib in subjects with advanced nonadipocytic STS.
 
The study will be conducted in compliance with International Conference on Harmonization (ICH) Good Clinical Practices (GCPs).
 
Dose-finding Phase 1 Portion of the Study:
 
Dose levels of nab-Sirolimus will be tested in cohorts of 3 subjects each using the 3+3 dose-finding design. A summary of dose levels and cohorts are provided in Table 1 and Table 2.
 
Phase 2 Portion of the Study:
 
This will be conducted using Simon's two-stage design. Subjects enrolled in the phase 1 study at the RP2D cohort will be included for response and safety evaluation in phase 2.

STUDY DRUG ADMINISTRATION	
Subjects will receive nab-Sirolimus by IV infusion over a minimum of 30 (+10) minutes at 100, 75, 60, 45, 30, 20, or 15 mg/m^2 either Days 1 and 8 in a 21-day cycle or on Day 1 only in a 21-day cycle.
 
Pazopanib will be given per standard of care guidelines, daily. Pazopanib dosing may be initiated at 400, or 800 mg once daily by mouth, without food (at least 1 hour before or 2 hours after a meal). Pazopanib starting dose must remain consistent within a dose-finding cohort.
 
Subjects will continue therapy until unequivocal clinical disease progression, unacceptable toxicity, until in the opinion of the investigator the subject is no longer benefiting from therapy, or at the subject's discretion.

TABLE OF CONTENTS

PROTOCOL SYNOPSIS.....	3
LIST OF ABBREVIATIONS AND DEFINITIONS OF TERMS.....	11
1. INTRODUCTION.....	15
1.1. Soft Tissue Sarcomas .....	15
1.2. Nab-Sirolimus Background .....	16
1.2.1. Rapamycin and Rapalogs .....	16
1.2.2. Nab-Sirolimus (ABI-009, nab -Rapamycin) .....	17
1.2.3. Preclinical Studies with nab-Sirolimus.....	17
1.2.4. Clinical Studies with nab-Sirolimus.....	19
1.3. Pazopanib in Soft Tissue Sarcoma .....	20
1.4. Rationale for Combination of nab-Sirolimus with Pazopanib for Nonadipocytic Soft Tissue Sarcoma.....	20
1.5. Rationale for Starting Dose Selection and Schedule of nab-Sirolimus and Pazopanib.....	21
2. STUDY OBJECTIVES AND ENDPOINTS .....	23
2.1. Objectives .....	23
2.2. Endpoints .....	23
2.3. Study Design .....	24

## LIST OF ABBREVIATIONS AND DEFINITIONS OF TERMS

AE	adverse event
ALP	alkaline phosphatase
ALT	alanine transaminase (SGPT)
ANC	absolute neutrophil count
AST	aspartate transaminase (SGOT)
AUC	area under the time-concentration curve
BSA	body surface area
C max	maximum plasma drug concentration
C min	minimum plasma drug concentration
CBC	complete blood count
CI	confidence interval
CNS	central nervous system
CR	complete response
CT	computed tomography
DLT	dose-limiting toxicity
DMC	data monitoring committee
DNA	deoxyribonucleic acid
DCR	disease control rate
DOR	duration of response
ECOG PS	Eastern Cooperative Oncology Group performance status
CRF	electronic case report form
EOS	end of study
EOT	end of treatment
GCP	Good Clinical Practice
G-CSF	granulocyte-colony stimulating factor
ICH	International Conference on Harmonisation
IEC	Independent Ethics Committee
IHC	Immunohistochemistry
IND	investigational new drug
IP	investigational product

IRB	Institutional Review Board
MedDRA	Medical Dictionary for Regulatory Activities
mg	milligram
mL	milliliter
MRI	magnetic resonance imaging
MTD	maximum-tolerated dose
mTOR	mammalian target of rapamycin
NCI CTCAE	National Cancer Institute Common Terminology Criteria for Adverse Events
ORR	overall response rate
OS	overall survival
PD	progressive disease
PFS	Progression-free survival
PK	pharmacokinetics
PR	partial response
PTEN	protein tyrosine phosphatase
RECIST	Response Evaluation Criteria in Solid Tumors
SAE	serious adverse event
SD	stable disease
SGOT	serum glutamic oxaloacetic transaminase (AST)
SGPT	serum glutamic pyruvic transaminase (ALT)
TBL	total bilirubin level
ULN	upper limit of normal

Abbreviation or Term	Definition/Explanation
Study Day 1	First day that protocol-specified IP is administered to the subject.
End of Treatment	The date of the last dose of ABI-009 or pazopanib, whichever is later for an individual subject.
End of Treatment Visit	For a subject is when safety assessments and procedures are performed after the last treatment, which should occur within 1 week ( $\pm 3$ days) after the last dose of ABI-009 or pazopanib, whichever is later.
30 Day Follow-Up Visit	For a subject is when safety assessments and procedures are performed after the End of Treatment visit. The 30-Day Follow-Up visit should occur 30 days (+/- 7 days) after the last dose of ABI-009 or pazopanib, whichever is later.
End of Study	Either the date of the last visit of the last subject to complete the study, or the date of receipt of the last data point from the last subject that is required for primary, secondary, and/or exploratory analysis, as pre-specified in the protocol.
Follow-up Period	The on-study time period after the 30-Day Follow-Up Visit. All subjects that discontinue study drug and have not withdrawn full consent to participate in the study will continue in the follow-up phase for survival and initiation of new anticancer therapy. Follow up will continue approximately every 12 weeks ( $\pm 3$ weeks) from the 30-Day Follow-Up Visit, or more frequently as needed, until death, withdrawal of consent, or the study closes, whichever is the earliest. This evaluation may be made by record review and/or telephone contact.
Primary Analysis	For this study will occur after all subjects have either completed the study or completed 12 months of treatment. Subjects who are still active at the time of the primary analysis may continue on study until disease progression or medication intolerance is observed.
Efficacy Analysis Dataset	All enrolled subjects with measurable tumor per RECIST v1.1 at baseline who received at least 2 doses of ABI-009 and had a follow-up CT / MRI (modified treated population).

Full Analysis Set	All enrolled subjects who receive at least 1 dose of ABI-009 (treated population).
Per-protocol Analysis Set	All enrolled subjects who do not have any prospectively defined protocol violations.
Progression-free survival	The time from the first dose date to the first observation of a disease progression or death due to any cause.
Overall survival	The time from the first dose date to the date of death due to any cause.
Overall response rate	The proportion of subjects who achieve a confirmed partial response or complete response per RECIST v1.1. Response rates based on a local radiologic assessment.
Duration of response	The time from when criteria of response are first met until the first observation of disease progression per RECIST v1.1 or death due to any cause, whichever comes first.

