### **9.3. Efficacy Analysis**

Subjects will be evaluated for ORR, DCR, or progressive disease (PD) by CT imaging. Contrast enhanced MRI can also be used if CT is contra-indicated, as long as the same modality is used throughout the study. Baseline scan results can be accepted from outside institutions but must be done within 4 weeks of starting therapy and must include (as clinically indicated), chest abdominal, and pelvic CT or MRI. The first response assessment by CT or MRI scans documenting target lesions will be done 6 weeks after C1D1 and should be repeated every 6 weeks for the first year, then every 12 weeks thereafter until the end of treatment. If an initial observation of objective response (CR or PR) is made, a confirmation scan should be done at 6 weeks after initial observation. Scans should continue on schedule regardless of delays in nab-Sirolimus dosing.

The efficacy endpoints of ORR (CR + PR), DCR (CR, PR, and SD  $\geq 18$  weeks), and PFS will be determined by a local radiologic assessment using RECIST v1.1. After the 30-Day Follow Up Visit, subjects will be followed for survival every 12 weeks ( $\pm 3$  weeks), or more frequently as needed, until death, withdrawal of consent, or the study closes, whichever is the earliest.

The number and percentage of subjects achieving response ORR, DCR, or progressed will be summarized.

Median PFS and OS will be summarized using Kaplan-Meier (KM) analysis. Analysis of other efficacy endpoints, PFS rate at 3 and 6 months, and OS rate at 12 months will be assessed via descriptive statistics, for the number of subjects is expected to be small.

Response duration usually will be measured from the time of initial response until documented tumor progression.

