### **9.5. Sample Size Considerations**

**Phase 1:** Up to 49 subjects to identify the MTD, but the MTD may be reached with as few as 22 subjects. Subjects who discontinue from the study prior to completing the DLT assessment window for reasons other than toxicity will be replaced at the same dose level.

**Phase 2:** For sample size determination, we assume the following:

1. For aa-TKI/pazopanib monotherapy in nonadipocytic STS, the baseline anticipated PFS rate at 3 months is approximately 50%.
2. An increase by the combination therapy of the PFS rate at 3 months to 70% would be considered clinically meaningful.
3. This is an exploratory phase 1/2 study. Thus, type I (false positive) errors are less worrisome than type II (false negative). We therefore set alpha=0.1 for rejection of null hypothesis. Beta is set at 0.1 (90% power), again, to minimize type II errors.
4. We are using a Simon's two-stage study design for the phase 2 efficacy evaluation.

In the first stage, at least 23 subjects would be enrolled, including the 3-6 subjects from phase 1 at the RP2D. If at least 11 were progression-free at the 3 months evaluation, then additional subjects would be enrolled to a total of 39 subjects in Phase 2. If at least 23 were progression-free at 3 months, then this would provide preliminary data to indicate that the combination was active and worthy of further evaluation in this clinical setting.

Subjects who fail to become evaluable for the secondary endpoint with a follow-up CT/MRI will be replaced.

To assess the primary endpoint, we elected to use a Simon's minimax design. This was selected to be most conservative in evaluable subjects needed to answer the primary hypothesis. In this case, a total of 39 evaluable subjects will be required in the phase II component of the study, if it extends through both stages.

This type of design has greater statistical power than a single-arm design. For example, a single arm trial enrolling the same number of subjects (n=39) would only have a statistical power of 82%, versus 90% for the proposed design. Alternatively, it would require 50 evaluable subjects in a single-arm design to achieve the desired 90% power.

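### The denominator of the primary 3-month PFS rate is inconsistent (enrolled versus evaluable), and under the evaluable reading early deaths can be replaced out of the Simon count

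*Combined protocol and SAP*

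**What the plan says.** The definitions list starts the PFS clock at first dose and counts any death: "The time from the first dose date to the first observation of a disease progression or death due to any cause". The same list defines two sets that could serve as the denominator, besides a per-protocol set:

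- The Efficacy Analysis Dataset requires measurable disease at baseline and is limited to subjects "who received at least 2 doses of ABI-009 and had a follow-up CT / MRI (modified treated population".
- The Full Analysis Set is "All enrolled subjects who receive at least 1 dose of ABI-009 (treated population".

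Neither is tied to the 3-month PFS rate. Section 9.3 says only that "PFS rate at 3 and 6 months, and OS rate at 12 months will be assessed via descriptive statistics". The one set that Section 9 does assign is the safety set (Section 9.2).

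Sections 3.1 and 9.5 express both Simon stages in enrolled subjects: at least 23, then a total of 39. The rules are "If at least 11 were progression-free at the 3 months evaluation" for continuing and "If at least 23 were progression-free at 3 months" for activity. Section 5.2 treats a subject as enrolled at the first nab-Sirolimus dose; Section 5.1 ties enrolment to the eligibility decision and a completed packet. Section 9.5 then says, for the primary hypothesis, that "a total of 39 evaluable subjects will be required in the phase II component of the study", and also that "Subjects who fail to become evaluable for the secondary endpoint with a follow-up CT/MRI will be replaced". It does not define evaluable for the primary endpoint.

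**The concern.** A death in week 4 is a failure under the PFS definition. The first scheduled scan is at week 6 (±1 week), so that subject has no follow-up scan, falls outside the only efficacy-named set, and meets the replacement condition in Section 9.5. If evaluable subjects form the Simon count, the failure is exchanged for someone who reached a scan. The rate is then biased upward and both cut-offs become easier to pass. In an open-label, single-arm study with local radiologic reading, a denominator left open can also be settled after results are known.

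**Working it through.** **Inputs.** From Section 9.5: null rate 50%, target rate 70%, alpha 0.1, power 90%, 23 subjects in stage 1, 39 in total, printed cut-offs 11 and 23. Assumed, because the documents do not give them: f, the share of treated subjects who are dropped and replaced, and g, the share of those who are true 3-month failures. The true rate among treated subjects is taken as 50%.

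**Step 1: reproduce the design.** With continue-cut a1 and final cut a,

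P(declare active | p) = Σ over x ≥ a1 of Bin(x; 23, p) × P(Y ≥ a − x), with Y ~ Bin(16, p).

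- Cut-offs ≥12/23 and ≥24/39: 0.0978 at p = 0.5 and 0.9015 at p = 0.7. A minimax search returns this design, so the plan's sizes and power reproduce.
- Printed cut-offs ≥11/23 and ≥23/39: 0.1667 at p = 0.5 and 0.9486 at p = 0.7. These exceed alpha 0.1 with nobody replaced. That is a separate defect and is not counted here.

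**Step 2: the rate among those who remain.** Dropping a share f, of whom g are failures, gives

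p* = (0.5 − f(1 − g)) / (1 − f).

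For g = 1: 0.50/0.97 = 0.5155 at f = 3%; 0.50/0.95 = 0.5263 at 5%; 0.50/0.90 = 0.5556 at 10%. For g = 0.75: (0.5 − 0.0075)/0.97 = 0.5077 at 3%; (0.5 − 0.0125)/0.95 = 0.5132 at 5%. For g = 0.5, p* stays at 0.5. The expected number replaced to reach 39 is 39/(1 − f) − 39: 1.2, 2.1 and 4.3 subjects at 3%, 5% and 10%.

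**Step 3: type I error at p*.**

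| f | g | ≥12/23, ≥24/39 | Printed ≥11/23, ≥23/39 |
|---|---|---|---|
| 0 | – | 9.8% | 16.7% |
| 3% | 1 | 13.5% | 22.0% |
| 5% | 1 | 16.7% | 26.2% |
| 10% (illustrative upper case) | 1 | 27.4% | 39.4% |
| 3% | 0.75 | 11.5% | 19.2% |
| 5% | 0.75 | 12.9% | 21.1% |
| any | 0.5 | 9.8% | 16.7% |

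At g = 1 and f = 3% or 5%, replacement adds 0.1354 − 0.0978 = 3.8 points or 0.1671 − 0.0978 = 6.9 points with the alpha-holding cut-offs. With the printed cut-offs it adds 0.2196 − 0.1667 = 5.3 points or 0.2619 − 0.1667 = 9.5 points.

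**Step 4: what drives it.** The cut-offs are absolute counts. Dropping a failure without replacing that subject adds nobody who could be progression-free, so neither cut becomes easier to reach. Only replaced failures inflate the error. As an example, 23/39 is 59.0%; with two replaced failures put back it is 23/41 = 56.1%.

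**The case against.** The best defence is that the decision rules speak of enrolled subjects, Section 5.2 dates enrolment from first dose, and PFS runs from first dose. On that reading the denominator is in effect the Full Analysis Set, and the efficacy-named set, with its scan requirement, serves response and disease control. The replacement sentence supports this, since it is worded for the secondary endpoint. This is a coherent reading with real textual support, and under it there is no inflation. But no passage states it, and Section 9.5 itself moves to evaluable subjects when it turns to the primary hypothesis.

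Other limits also stand. ECOG 0–1 and a life expectancy above 3 months make early death less likely, though not impossible. Subjects who stop for reasons other than progression are due an end-of-treatment scan, so many of them would not lack a follow-up scan. Neither f nor g is known.

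A reader might infer that the protocol orders early deaths to be excluded; it does not. Nor does it replace everyone with fewer than two doses. On the Day-1-only schedule the second dose is due on day 22, and missing it puts a subject outside the efficacy-named set, but Section 9.5 replaces only for a missing scan.

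**Conclusion.** The denominator of the primary endpoint is inconsistent, and one available reading lets early deaths leave the Simon count and be replaced, against the protocol's own PFS definition. With cut-offs that hold alpha, about one or two replaced failures (f = 3% or 5%) move type I error from 9.8% to 13.5% or 16.7%. If three-quarters of those replaced are failures it is 11.5% or 12.9%; if half are, there is no change. These figures assume the evaluable reading, actual replacement and a true 50% rate among treated subjects.

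It would be tempting to cite the 39.4% in the table as the effect of this problem. That needs the printed cut-offs, whose 16.7% baseline has another cause, and an assumed 10% loss made up wholly of failures. Nor is the absence of a rule for unknown 3-month status, or for clinical progression without a scan, part of this error; those are choices the sponsor still has to state.

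**What to change.** In the definitions list and Sections 9.3 and 9.5:

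- Name the Full Analysis Set at the recommended phase 2 dose (at least one dose) as the denominator for both Simon decisions, and use one term throughout.
- Count every death or RECIST progression before the 3-month assessment as not progression-free, with or without a follow-up scan, and do not replace these subjects in the primary analysis.
- Keep the Efficacy Analysis Dataset for response endpoints and as a sensitivity analysis for PFS.

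This is wording only; the set already exists and the sizes stay at 23 and 39. The cost is a slightly less favourable observed rate.

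Separately, the sponsor should choose and state in advance one rule for unknown 3-month status and one for unscanned clinical progression. Scoring unknown status as failure is one option, and it costs power: putting 0.7 × (1 − u) into the step 1 formula, the ≥12/≥24 cut-offs fall from 90% to 84% at u = 3% missing and 79% at 5%. That matters in a plan that treats type II error as the worse one. Table 5 note k and Section 5.2.4 limit the end-of-treatment scan to stops for reasons other than disease progression, while Section 5.3 says progression per RECIST v1.1. These passages must be reconciled.

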## 1. INTRODUCTION

### 1.1. Soft Tissue Sarcomas

Soft tissue sarcoma (STS) is a relatively rare and histologically diverse neoplasm of mesenchymal origin, occurring with an incidence of about 1% of all adult cancers, and includes >70 histologic subtypes. For localized resectable disease, surgical resection is the standard of care, and for unresectable sarcomas, radiation therapy is offered. However, recurrence rate is high (~50%) and treatment options for metastatic/relapsed STS are limited to anthracycline-based chemotherapy (i.e., doxorubicin), administered alone or in combination with alkylating agents (ifosfamide and/or dacarbazine). However, drug resistance and toxicities often limit benefits of chemotherapy used to treat metastatic sarcomas.

Recently, in 2015, 2 therapeutics were approved by the United States Food and Drug Administration (US FDA) for STS, pazopanib (Votrient®, Novartis Pharma) and trabectedin (Yondelis®, Janssen Biotech, Inc.). Pazopanib is a multiple tyrosine kinase inhibitor (TKI), which hinders growth factor-mediated signal transduction pathways involved in tumor angiogenesis, and was approved for nonadipocytic STSs refractory to chemotherapy. Trabectedin, a natural alkaloid which interferes with gene transcription and DNA repair, was approved for liposarcoma and leiomyosarcoma. Although the new therapeutic options offer improvement of the course of disease in specific subtypes of STSs, the prognosis of advanced disease has remained uniformly poor, with an estimated median survival of only 8 to 13 months, and more efficacious therapeutics options are needed.

